### **I. Objectives and Introduction:**

In recent years, the number of young patients having atypical endometrial hyperplasia (EAH) and early endometrial cancer (EC) has been gradually increasing. EAH is a precancerous stage of EC, and the risk of developing EC from EAH is the highest (8%~30%). [1, 2] Women who and EC and are younger than 40 years of age account for 2% to 14% of all cases, among whom 70% are nulliparous. [2-5] These women are generally reluctant to undergo a total hysterectomy that would result in loss of fertility; instead, they prefer conservative treatment of EC and EAH.

The conservative treatment for young women with EC and EAH who desire to conceive has remained challenging. Some reports have revealed that oral highly active progestogens are effective as a conservative treatment option. [2] However, traditional treatments as such often have many and severe side-effects and contraindications including thromboembolism and hypertension, and complications including obesity, ovarian dysfunction such as polycystic ovary (PCO) syndrome, and fasting hyperglycemia. [6] These side-effects and contraindications often lead to withdrawal from therapy. Therefore, a new conservative treatment that is largely effective and widely applicable and has relatively mild side effects, is urgent needed.

On the one hand, levonorgestrel-releasing intrauterine system (LNG-IUS) has protects endometria and inhibits its hyperplasia; and on the other hand, it elevates local drug concentration with fewer and milder side-effects and contraindications, more convenient administration, and better effects than oral progestogens in theory. The use of LNG-IUS for the fertility-preserving treatment of EC and EAH has been proposed in many guidelines,[3, 5, 7-12] in which LNG-IUS was suggested as first-line medicine treatment for EAH by RCOG-BSGE. [1] Nevertheless, no appropriately designed randomized controlled trial (RCT) has been identified that investigates the optimal dosage, duration of treatment, lesion regression, and pregnancy rate after therapy in young women with EC and EAH, with regard to the use of LNG-IUS in particular. Therefore, we conducted the current prospective phase II study on fertility-preserving treatment of EC and EAH.

This RCT will be carried out at West China Second University Hospital between January, 2018 and December, 2020. Based on the inclusion and exclusion criteria of this study, patients with EAH or EC at stage IA and a strong desire to get pregnant will be considered for enrollment. The enrolled patients will be allocated to one of the arms by central randomization. Drugs including the LNG-IUS, oral highly active progestogen (medroxyprogesterone acetate, or MPA), and gonadotropin-releasing hormone agonists (GnRH-a) will be used in this trial. All these drugs were included in not only the abovementioned guidelines but also other guidelines such as ACOG-SGO and JSGO.[13, 14] The objective of this trial is to assess the efficacy of fertility-preserving treatment of EC and EAH in young women using LNG-IUS by analyzing the therapeutic effects, pregnancy rate, and birth rate among different treatment groups.

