#### **1. Primary End Points:**

There are two aspects to the primary end points of the study and as follows:

- 1) To value the efficacies of LNG-IUS as fertility-preserving treatment for early EC and EAH by pathologic response. Pathologic response to medicine treatment is categorized as complete response (CR), partial response (PR), no change (NC), and progressive disease (PD). CR is defined as the absence of any hyperplastic or cancerous lesion. PR is defined as the residual lesion with degeneration and atrophy of endometrial glands. NC is defined as residual lesion without degeneration or atrophy of endometrial glands. PD is defined as the appearance of endometrial cancer for EAH and grade 2 (G2) or 3 for EC.
- 2) To compare the rate of pregnancy and alive baby delivery.

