## **II. Methods and Process**

### **1. Participants Recruitment:**

All participants will be recruited from West China Second University Hospital between January, 2018 and December, 2020 based on the inclusion and exclusion criteria of this study. All participants will have signed the informed consent form.

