**Comments:**

(1) The basic history collection includes detailed history of prior treatment; with or without contraindications of oral highly active progestogens: hypertension, diabetes (DM), liver function damage, thrombotic disease and so on; with or without reproductive endocrine disease: infertility, PCO syndrome, insulin resistance (IR), impaired fasting glucose (IFG) and so on; with or without any other system disease; surgical history, allergy history; family history especially for carcinomas.

(2) The basic endocrine examinations include sex hormone, anti mullerian hormone (AMH), and insulin release test (IRT) to rule out PCO syndrome, IR, IFG, and DM. Follow-up treatment will be provided when necessary.

(3) If the patients have abnormality in breast ultrasound, she needs to visit the Department of Breast Surgery to evaluate the risk of continuous progesterone treatment.

(4) Based on the inclusion and exclusion criteria of this study, the patients are allocated to one of the arms by central randomization with study site allocation. The arms and interventions and the probability of distribution are as follows:

1) If the patients does not have thromboembolism, liver dysfunction, hypertension, or diabetes, she will be assigned to one of the following two groups, with a probability of 50%, respectively: a) sequential oral medroxyprogesterone acetate (MPA) 500mg QD group; and b) LNG-IUS (Mirena®) group.

2) If the patients are diagnosed of thromboembolism, liver dysfunction, hypertension, or diabetes, she will be assigned to one of the following two groups, with a probability of 50%, respectively: a) intramuscular injection of leuporelin acetate microspheres (GnRH-a) + LNG-IUS group; and b) LNG-IUS (Mirena®) group.

(5) For the groups of oral highly active progestogens, medicine treatment should only be continued if the liver function is normal, which is evaluated by monthly tests.

(6) For the groups of LNG-IUS, the medical device needs to be replaced by a new one on every hysteroscopy to insure adequate drug release

(7) Endometrial tissue sampling for diagnosis should be performed by hysteroscopy every 3 months, and the histologic diagnoses of all specimens are made by two categorized pathologists.

[figure not shown]

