(8) After 6 months' continuous progestogen-based therapy, if the patients has PR/NC, progestogen-based therapy should be continued for one more cycle (3 months), and if the patient still has PR/NC, she will withdraw from this trial and undergo hysterectomy; if the patients has CR at the second or third endometrial evaluation, fertility treatment will be initiated immediately; and if the patients has documented progression on the biopsies at any time, the protocol treatment will be stopped and hysterectomy be recommended.

(9) The option of natural conception or assisted reproduction should be discussed with the fertility specialist in the reproduction center of our hospital; assisted reproduction is recommended if the patients 1) has history of infertility; 2) has risk factors for infertility such as PCO syndrome, obesity, diabetes, and lack of ovulation; or 3) suffers from failed pregnancies after 6 months of natural conception.

- (10) If the patient succeeds in conceiving, she will receive professional prenatal examinations from the obstetrics specialist in our hospital.
- (11) All the professors in the Department of Obstetrics and Reproductive Center of our hospital are on this research team.
- (12) Long-term follow-up will proceed even after treatments are finished, and corresponding clinical treatments will be provided for patients with different conditions.

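### The trial's run dates and its recruitment window are identical, and no end of follow-up is set for the primary pregnancy and live-birth end point

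*Combined protocol and SAP*

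**What the plan says.** Two sections give dates, and they are the same. Section I (Objectives and Introduction): "This RCT will be carried out at West China Second University Hospital between January, 2018 and December, 2020". Section II.1 (Participants Recruitment): "All participants will be recruited from West China Second University Hospital between January, 2018 and December, 2020".

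There are two primary end points (section I.1). The first is histological: "To value the efficacies of LNG-IUS as fertility-preserving treatment for early EC and EAH by pathologic response". The second is reproductive: "To compare the rate of pregnancy and alive baby delivery". No assessment time is attached to the second.

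The route to a birth is set out in the comments to sections 3.1 (EAH) and 3.2 (EC). Sampling is three-monthly: "Endometrial tissue sampling for diagnosis should be performed by hysteroscopy every 3 months". If the woman "has CR at the second or third endometrial evaluation, fertility treatment will be initiated immediately"; Tables 1 and 2 place those evaluations at months 6 and 9. One of the grounds for recommending assisted reproduction is that she "suffers from failed pregnancies after 6 months of natural conception".

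On what happens afterwards, the last comment in each section says "Long-term follow-up will proceed even after treatments are finished". It gives no duration, visits or data cut-off, and does not mention the pregnancy end point. Tables 1 and 2 end at month 9. Section III.3 assigns survival analysis to the primary end points without defining the event, the time origin or the censoring rule.

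**The concern.** Read literally, the last woman may be randomised in the month the trial closes. A live birth cannot occur until treatment has produced a complete response, conception has followed and the pregnancy has been carried. A woman entering in the second half of the window may therefore have little or no chance of contributing a birth by the closing date.

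If outcomes stopped being collected then, a crude live-birth rate would count many women as having no birth only because they had not been observed long enough. It would rest on early recruits and quick conceivers. If collection continues, the plan does not say until when, so the analysis date for a primary end point is left open and could be chosen after results are known. Either way, a primary end point has no defined observation period.

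**Working it through.** The plan states no figure for the share of women who can be followed to delivery, so there is none to reproduce.

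**Inputs from the documents**
- Window: January 2018 to December 2020, 36 months (sections I and II.1).
- Start of fertility treatment: month 6 or month 9 (comment 8 in section 3.1, comment 11 in section 3.2).
- Natural conception before assisted reproduction is recommended on that ground: 6 months (comments 9 and 12).
- Sample size (section III.1): 3 × 18 + 2 × 30 + 2 × 14 + 2 × 20 = 182.

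**Assumptions**
- Gestation of 9 months (range 8.5 to 9.5).
- Even accrual over the 36 months (varied in step 2).
- No outcome collected after December 2020 (relaxed in step 3).

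**Step 1. Share of women who enter too late.** If a path from randomisation to delivery takes m months, the share is m/36.

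| Path | m | Share |
|---|---|---|
| CR at month 6, immediate conception | 6 + 9 = 15 | 41.7% (about 76 of 182) |
| CR at month 9, immediate conception | 9 + 9 = 18 | 50.0% |
| CR at month 6, 6 months to conceive | 6 + 6 + 9 = 21 | 58.3% |
| CR at month 9, 6 months to conceive | 9 + 6 + 9 = 24 | 66.7% |

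For the fastest path, gestation of 8.5 to 9.5 months gives 40.3% to 43.1%. For the month-9 evaluation itself the share is 9/36 = 25%; for month 6 it is 6/36 = 17%.

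**Step 2. Accrual shape, 15-month path.** Linearly rising accrual: 1 − (21/36)² = 66%. Linearly falling accrual: (15/36)² = 17%.

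**Step 3. Follow-up continuing k months past December 2020.** The share becomes max(0, m − k)/36. For the four paths in order:
- k = 12: 8.3%, 16.7%, 25.0%, 33.3%
- k = 15: 0%, 8.3%, 16.7%, 25.0%
- k = 24: 0% in all four

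**Step 4. Crude rate against survival analysis under a December 2020 stop.** This is a simulation of 400,000 women with even accrual. All clinical inputs are assumed: CR in 60% at month 6 and in 40% of the rest at month 9, 5% conception per month, up to 24 months of trying, 75% of pregnancies ending in live birth, and 9 months of gestation.
- Crude: a true live-birth rate of 40% is recorded as 12%. About 29% of births and 54% of pregnancies are seen.
- Sensitivity: with 3% and 10% monthly conception (the latter with 70% CR at month 6 and 80% live birth), 27% and 35% of births are seen. In the base case, falling or rising accrual gives 47% or 12%, and a 12-month limit on trying gives 40%.
- Kaplan-Meier, censored only at the closing date: birth by 24 months is estimated at 19.9% (true 19.9%), and birth by 33 months at 33.5% (true 33.6%). Women without a response stay in the risk set until the closing date.

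**Step 5. Numbers behind the late part of the curve.** With even accrual, the expected number per group with at least m months of observation is n × (36 − m)/36. At m = 27 this is 14 × 9/36 = 3.5 up to 30 × 9/36 = 7.5. At m = 33 it is 14 × 3/36 = 1.2 up to 30 × 3/36 = 2.5. These counts are before any dropout, hysterectomy or earlier birth. The 27-month mark corresponds to 9 months of treatment, 6 of natural attempts, about 3 of assisted reproduction (an assumption) and 9 of gestation.

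**The case against.** The strongest reply is that a December 2020 data stop is an inference. The introductory sentence is general, and the recruitment section ties the dates to enrolment. Follow-up is promised beyond treatment, consent includes agreement to follow-up, and pregnant women receive antenatal care in the same hospital. This stands: no section ends outcome collection in December 2020, so every share in step 1 is conditional. Fifteen further months would remove the problem for the fastest path. But the promise does not supply a length, a schedule or a cut-off, and those are what the end point lacks.

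A second reply is that survival analysis is planned and that late entry falls alike on arms randomised together. This also stands, and step 4 bears it out: administrative censoring alone does not bias the curve. What remains is precision, given the counts in step 5. The result also depends on a censoring rule the plan does not contain. Women who leave for hysterectomy must be counted as having no birth, not censored when they leave.

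A reader might infer that the live-birth comparison cannot be answered, or that women needing a third cycle or assisted reproduction are nearly all lost. The documents do not support either. Even with a hard stop, 21/36 = 58% of women have the 15-month minimum, and half have the 18 months that a third-cycle woman who conceives promptly would need. Nor does the 6-month natural attempt apply to everyone: assisted reproduction is recommended directly for women with a history of, or risk factors for, infertility.

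Counting the screening hysteroscopy as the first evaluation would shorten the fastest path to 12 months (12/36 = 33%). The reference to 6 months of therapy and the response-evaluation row of the tables point to month 6 instead.

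**Conclusion.** The concern holds as a defect in the plan's dates and follow-up. The run dates coincide with the recruitment window, and a primary end point that cannot occur before about month 15 has no end of follow-up.

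The size is conditional. If collection stops in December 2020 and accrual is even, about 42% of women enter too late for the fastest delivery (17% to 66% across the accrual shapes tried), and 25% miss the month-9 evaluation. Crude live-birth rates would then be well below the true rates. By how much depends on assumed response and conception rates. A properly censored survival analysis would be unbiased but imprecise and weighted to early births, because very few women per group would be at risk at the relevant times. Pathologic response is much less affected.

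This is more than missing detail, because the dates as written conflict with a primary end point. It does not show that the comparison is impossible, or that the sponsor intends to stop collecting data in December 2020.

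**What to change.** - In sections I and II.1, state that January 2018 to December 2020 is the recruitment window only.
- Add a separate end of follow-up, with one horizon from randomisation for every randomised woman, for example pregnancy by 24 months and live birth by 24 + 9 = 33 months.
- In section III.3, state the data cut-off and administrative censoring at it, and say how women who leave for hysterectomy are counted.
- Report pathologic response once the last woman passes month 9, and pregnancy and birth once the last woman reaches the horizon.
- If the trial must close in December 2020, declare pregnancy and live birth descriptive. Stopping recruitment early enough is not realistic with a 33-month horizon, since it would leave 36 − 33 = 3 months to enrol.

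The cost is an amendment to the text, a simple contact schedule within the follow-up already promised, and a delay of about 2 to 3 years for the pregnancy and birth results. The response results need wait only for the last month-9 evaluation.

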#### **1. Primary End Points:**

There are two aspects to the primary end points of the study and as follows:

- 1) To value the efficacies of LNG-IUS as fertility-preserving treatment for early EC and EAH by pathologic response. Pathologic response to medicine treatment is categorized as complete response (CR), partial response (PR), no change (NC), and progressive disease (PD). CR is defined as the absence of any hyperplastic or cancerous lesion. PR is defined as the residual lesion with degeneration and atrophy of endometrial glands. NC is defined as residual lesion without degeneration or atrophy of endometrial glands. PD is defined as the appearance of endometrial cancer for EAH and grade 2 (G2) or 3 for EC.
- 2) To compare the rate of pregnancy and alive baby delivery.

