### **III. Statistical Analysis Plan**

#### **1. The Sample Size Calculation:**

This clinical study is a RCT and aims to evaluate the fertility-preserving treatments for young women having EAH and EC. Experimental stratification is conducted based on whether the participants have contraindications of oral highly active progesterone (including thromboembolic disease, liver dysfunction, hypertension, and diabetes). The distribution ratio between the experimental group and the control group is 1:1. The estimated sample size can detect difference under  $\alpha = 0.05$  and Power = 0.8, calculating the exact sample size and randomizing grouping. For EC without contraindications of oral highly active progestogens, we will compare sample rates among the three groups by using the PASS software and will calculate the sample size of 18 cases for each group. For EC with contraindications of oral highly active progestogens, we will compare sample rates between the two groups by using the PASS software and will calculate the sample size of 30 cases for each group. Similarly, the calculation of sample size for patients having EAH with and without contraindications of oral highly active progestogens are 14 and 20 cases for each group.

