#### **3. Statistics:**

SPSS software will be used for statistical analysis. Survival analysis is used for primary end points and chi-square test for secondary end points.

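### Does having response, pregnancy and live birth all primary, with no success rule or testing order, inflate the false-positive rate enough to require a change?

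*Combined protocol and SAP*

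**What the plan says.** Section I, Primary End Points, states "There are two aspects to the primary end points of the study and as follows". The first aspect is pathologic response, graded as complete response (CR), partial response, no change or progression. The second is "To compare the rate of pregnancy and alive baby delivery". The general objective in Section I names the outcomes one by one: the treatments are to be assessed "by analyzing the therapeutic effects, pregnancy rate, and birth rate among different treatment groups".

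Section III.1 gives alpha 0.05 and power 0.8 as inputs to the sample size and ties them to no end point. For the three-group EC sub-trial it says only that "we will compare sample rates among the three groups by using the PASS software", giving 18 per group. The other sub-trials have two groups each: 30 per group (EC with contraindications to oral progestogens), 14 (EAH with) and 20 (EAH without).

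Section III.3 is two sentences long. The one on methods reads "Survival analysis is used for primary end points and chi-square test for secondary end points". Nowhere is there a success rule, a testing order, an alpha split or a statement that results are descriptive. The 1) and 2) in the end-point list are not described as an order.

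The outcomes are linked by the care pathway. Section II.3.1, comment (8), says "if the patients has CR at the second or third endometrial evaluation, fertility treatment will be initiated immediately", and Section II.3.2, comment (11), says the same for EC. Section I calls the study phase II.

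**The concern.** When several outcomes are all primary, the reader needs to know what counts as success. If any one significant result at 0.05 is enough, the chance of a false-positive primary result exceeds 5%. The outcomes can also disagree. Pregnancy depends on response, but also on fertility risk factors and use of assisted reproduction, so a sub-trial could differ on pregnancy and not on response. The plan does not say how to judge that case, and a rule chosen after seeing the data would be open to selection. On its face this is a randomised comparison with a declared alpha and power and no control over multiple primary outcomes.

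**Working it through.** **1. The plan's own figures.** The group sizes cannot be reproduced, because Section III.1 names no end point, rates, sidedness or dropout. The only response rates in the document are background figures in Section V: 90% vs 69% regression in EAH. They are not declared as design inputs. Used as a yardstick, with mean rate (0.90 + 0.69)/2 = 0.795:

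n = [1.960 × √(2 × 0.795 × 0.205) + 0.842 × √(0.90 × 0.10 + 0.69 × 0.31)]² / 0.21² = (1.119 + 0.464)² / 0.0441 ≈ 57 per group.

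The plan has 20. This does not show that 20 is wrong. It does mean that the stated alpha and power cannot be tied to any one primary outcome, so alpha is a sizing input and not a promise about the whole set.

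**2. Error rate if any one success counts, independent tests at 0.05.**
- Two outcomes: 1 − 0.95² = 0.0975.
- Three outcomes: 1 − 0.95³ = 0.143 (upper bound 3 × 0.05 = 0.15).

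**3. The same with linked outcomes.** Pregnancy follows CR and live birth follows pregnancy, so the tests are positively correlated. Log-rank tests were simulated with no true difference (20,000 runs per setting, 96 settings) at the plan's group sizes. All event inputs are assumptions:
- CR 60, 70 or 85%, split 30/45/25% over months 3, 6 and 9.
- Pregnancy in 50 or 70% of those with CR, spread over 24 months.
- Live birth in 75% of pregnancies, nine months later.
- Follow-up 12–36 months; patients without CR either censored for pregnancy at month 9 or kept to the end.

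| Rule | Two-arm | Three-arm (global test) |
|---|---|---|
| Any of three | 0.104–0.139 | 0.120–0.149 |
| CR or live birth | 0.068–0.100 | 0.088–0.104 |
| Holm over three | 0.030–0.048 | 0.039–0.055 |
| Fixed sequence from CR | 0.047–0.055 | 0.050–0.056 |

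Requiring all three to be significant gives at most 0.003. A small part of the top values is small-sample test size, since single log-rank tests reach 5.6% (two-arm) and 6.2% (three-arm). A separate simulation with Fisher's exact test on proportions, two-arm, any one sufficient, gives 0.038–0.062 over three outcomes and 0.026–0.049 over two.

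The result therefore runs from below 0.5% to about 15%, depending on a rule and a test that the plan leaves open.

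**4. What a stated rule would cost.**
- *Fixed sequence, CR first.* At 20 per group and 90% vs 69%, CR power is 0.29–0.32 by log-rank (0.383 by exact Pearson). The gate stays shut in about 1 − 0.30 = 70% of trials. If pregnancy after CR truly differed (assumed 70% vs 30%), it could be claimed in 21% of trials.
- *Holm.* The same pregnancy difference is claimed in 39%, but CR power falls to 17–20%.
- *Equal alpha split.* An outcome with 80% power at 0.05 keeps Φ(1.960 + 0.842 − 2.241) = 71% at 0.025, or 66% at 0.0167. Restoring 80% multiplies n by (3.083/2.802)² = 1.21 for two outcomes, or 1.33 for three. For example, 20 becomes 25 or 27, and 30 becomes 37 or 41.
- *All must succeed.* No alpha is split, but joint power is 0.8² = 0.64 or 0.8³ = 0.51 if each outcome had 80% power independently. Positive correlation raises this.

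No rule is better on every count.

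**The case for a change.** The strongest opposing case is that a rule costs only wording. It needs no patients or visits, and without it the reading of discordant results can be chosen after the fact. The study declares alpha and power and never calls itself exploratory, so the phase II label is not a full answer. Section III.3 plans survival analysis, which makes log-rank more relevant than Fisher's test. Counting pregnancy and live birth as one aspect still leaves 7–10%.

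Much of this stands. The rule is missing, the arithmetic holds under its assumptions, and one sentence would make the report easier to read. What does not stand is the step from an unstated rule to an inflated error rate, because that requires an any-one-wins reading which the plan does not make. Nor is a sequence starting from CR as cheap as it looks. It would first require choosing CR out of a four-category response, and then a population, time origin and horizon for pregnancy and live birth, for which the protocol has only open-ended follow-up. Fertility outcomes are part of the stated objective, yet that sequence would usually remove them from confirmatory use. Since Holm, all-must-succeed or estimates alone would answer the point equally well, no particular amendment is called for.

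**Conclusion.** The omission is real but is a matter of missing detail. On a reading the plan does not state, the false-positive chance in a two-arm sub-trial is about 7–10% over two outcomes or 10–14% over three (three-arm global test 9–10% or 12–15%). On other readings it is at or near 5%, or far below. These figures rest on assumed response, pregnancy, live-birth and follow-up values, none of which the documents supply.

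In a single-centre phase II study with 14 to 30 per group, strict control across the primary outcomes is a choice, and each way of imposing it gives up power for response or for fertility. Analysts can fill the gap sensibly by reporting every primary outcome in each sub-trial with its estimate and confidence interval, and by not treating one isolated p-value below 0.05 as proof of success. The concern does not require a change to the plan.
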